10.2. Duration of Exposure to ABS eMDPI

Duration of exposure to ABS eMDPI (days and weeks) for the individual patient is the number of days the patient took at least 1 inhalation from the ABS eMDPI. Patients receive the ABS eMDPI devices at Baseline and subsequently by courier on Day 21. Duration of exposure is determined from all eMDPIs used by a patient and it is the total number of unique dates recorded by the eMDPIs from the dispense date and return date of a given device, inclusive. Note, if a patient uses more than 1 eMDPI device on a given day, it is still only 1 day of exposure for that given day. The patient's last date of contact or study completion date will be used as the device return date if the device return date is missing.

Duration of exposure (days and weeks) will be summarized using descriptive statistics overall, and by CE-COPD status and by CE-COPD severity.

Exposure to IMP, expressed in mcg units, will also be summarized using descriptive statistics. Average daily exposure, average weekly exposure, and the maximum exposure in a single day will be summarized overall, and by CE-COPD status and CE-COPD severity. One inhalation recorded by the ABS eMDPI is equivalent to 90 mcg.

10.3. Time on Study

Duration of time on study (days and weeks) will be summarized using descriptive statistics overall, and by CE-COPD status and by CE-COPD severity.

10.4. Adverse Events

All treatment emergent adverse events will be coded using the MedDRA (Medical Dictionary for Regulatory Activities). Adverse events will be included as treatment emergent based on the date of the baseline (ie, the earliest date an ABS eMDPI device was dispensed). Each patient will be counted only once in each PT or SOC category for the analyses of safety. Summaries will be presented for all adverse events (overall and by severity), adverse events determined by the investigator to be related to test IMP (ie, reasonable possibility [Table 5 in Section 7.1.4 of the protocol], defined as related or with missing relationship; overall and by severity), serious adverse events, CE-COPD related adverse events, and adverse events leading to withdrawal from the study, COPD exacerbations by severity, and COPD exacerbations by deterioration.

Patient listings for all adverse events, serious adverse events, and adverse events leading to withdrawal will be presented.

If any patient dies during the study, a listing of deaths will be provided, and all relevant information will be discussed in the patient narrative included in the CSR.

Any adverse event or serious adverse event with a missing start date will be considered treatment emergent.

10.5. Deaths

A listing of deaths by patient and narratives will be provided, if any patient dies during the study.

10.6. Clinical Laboratory Tests

Any patient who experiences menarche following screening will be required to have a negative urine pregnancy test prior to dosing with IMP. If a patient has a positive urine pregnancy test, then she will be discontinued from the study. A urine pregnancy test for women of childbearing potential will be performed at the Screening and Final/Early Termination visit.

A listing of urine pregnancy test by patient will be provided.

10.7. Physical Examinations

Physical examinations will be performed at the Screening, exacerbation visits, and Final/Early Termination visit.

A physical examination that includes, at a minimum, skin, lungs, cardiovascular, respiratory, gastrointestinal, and neurological assessments are completed at the Screening visit (eg, baseline values], exacerbation visits, and Final/Early Termination visit. Height (to be obtained at the Screening visit only) and weight will also be measured and recorded. Any pre-existing abnormality will be reported as a part of medical history and any ongoing abnormality identified at screening and any new findings or clinically significant change (worsening) identified at an exacerbation visit or the Final/Early Termination visit will be reported as an adverse event.

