Each use of the inhaler was generally high, as 209 patients (83%) in the PP population were somewhat to very satisfied with the study inhaler, with another 21 (8%) patients expressing neither satisfaction nor dissatisfaction. Other measures, such as ease of use and ease of dosing, generally showed satisfaction in about 90% of patients. The device was considered quite rugged as only 3 patients reported non-counter device issues, of which 2 were confirmed independently by the study site.

A total of 29 patients (8%) out of the 345 screened patients had 1 or more adverse events during the screening/run-in period and 85 patients (27%) out of the 316 included in the safety analysis set following enrollment into the study reported adverse events. There were no deaths reported in the study. Two patients had serious adverse events (atrial fibrillation and supraventricular tachycardia judged related to study drug in 1 patient, and skin eruption due to metformin in the second patient) while on study, and 1 patient was withdrawn due to an unrelated adverse event of sinusitis.

The most frequently occurring adverse event in the enrolled patients was headache in 4 patients during the run-in and 8 patients on study, followed by respiratory infections and disorders. These consisted of sinusitis in 7 patients, cough in 6 patients, upper respiratory infection in 6 patients, and nasopharyngitis in 4 patients while on study. The adverse events judged related to study drug were those commonly associated with albuterol products in the treatment of asthma, including abdominal pain, feeling jittery, irritability, weight increase, tremor, nervousness, coughing, and sneezing.

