7. ASSESSMENT OF SAFETY

In this study, safety will be assessed by qualified study personnel by evaluating reported adverse events and physical examinations.

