7.1. Adverse Events

7.1.1. Definition of an Adverse Event

Any untoward medical occurrence in a patient or clinical investigation subject administered a pharmaceutical product and which does not necessarily have to have a causal relationship with this treatment.

An adverse event can, therefore, be any unfavorable and unintended physical sign, symptom, or laboratory parameter that develops or worsens in severity during the course of this study, or significant worsening of the disease under study, or of any concurrent disease, whether or not considered related to the test IMP. A new condition or the worsening of a pre-existing condition will be considered an adverse event. Stable chronic conditions (such as arthritis) that are present before study entry and do not worsen during this study will not be considered adverse events.

Accordingly, an adverse event can include any of the following:

- intercurrent illnesses
- physical injuries
- events possibly related to concomitant medication
- drug interactions

All CE-COPD events require documentation by the Investigator in the CE-COPD Exacerbation Page in the eCRF. All evaluations entered into the CE-COPD exacerbation page require an in-person visit (Vz “Exacerbation Visit”, see [Table 1](#)). This visit can coincide with an unscheduled provider visit (Section [6.1.1](#)) or can be scheduled separately if an unscheduled provider visit has not occurred. Investigational centers must obtain source documentation of all exacerbations of COPD that occur during the treatment period to confirm the accuracy of the information obtained from the patient.

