9.7. Safety Analysis

Safety analyses will be performed on the safety analysis set (Section [9.2.3](#)).

Safety assessments and time points are provided in [Table 1](#).

All adverse events will be coded using the Medical Dictionary for Regulatory Activities. Each patient will be counted only once in each preferred term or System Organ Class category for the analyses of safety. Summaries will be presented for all adverse events (overall and by severity), adverse events determined by the investigator to be related to test IMP (ie, reasonable possibility [Section 7.1.4], defined as related or with missing relationship; overall and by severity), serious adverse events, and adverse events leading to withdrawal from the study. Patient listings of serious adverse events and adverse events leading to withdrawal will be presented.

The use of concomitant medications will be summarized by therapeutic class using descriptive statistics.

For continuous variables, descriptive statistics (number, mean, standard deviation, median, minimum, and maximum) will be provided for actual values and changes from baseline to each time point. For categorical variables, patient counts and percentages will be provided.

Descriptive summaries of serious adverse events, patient withdrawals due to adverse events, and

potentially clinically significant abnormal values (physical examination) based on predefined criteria will be provided as well.

If any patient dies during the study, a listing of deaths will be provided, and all relevant information will be discussed in the patient narrative included in the CSR.

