1. STUDY OBJECTIVES AND ENDPOINTS

1.1. Objectives and Endpoints

The objectives of this study are to explore the pattern and amount of albuterol use (as captured in the albuterol sulfate (ABS) multidose dry powder inhaler with an eModule (eMDPI), alone or in combination with other study data, preceding a moderate or severe CE-COPD (as diagnosed by the investigators per the protocol). The hypothesis is that albuterol use will increase several days prior to a moderate or severe CE-COPD and can serve as a marker of COPD deterioration.

The endpoints of the trial are the primary outcome measure (ie, CE-COPD) and the primary outcome predictor (ie, albuterol use) alone or in combination with secondary predictors (ie, other study data). These predictors of CE-COPD will be modeled to determine which patterns best predict the subsequent development of CE-COPD.

For albuterol use, parameters of interest will include (1) the total number of inhalations in the days preceding the peak of a CE-COPD, (2) the number of days prior to the peak of a CE-COPD when albuterol use increased, and (3) the number of albuterol uses in the 24 hours preceding a CE-COPD. Therefore, endpoints are not designated as either primary or secondary.

In addition to albuterol use, inspiratory flow values (maximal inhalational flow (MIF), inhalational volume, inhalation duration, and time to MIF), sleep disruption index (SDI), total daily steps (TDS), and baseline information regarding disease state and demographics will be studied. These data will be analyzed using both a univariate and multivariate approach, to determine which patterns best predict the subsequent development of a CE-COPD. Inspiratory flow values are obtained from the eMDPI, SDI is obtained for a subset of patients who agree to participate at specific investigational centers (n=100) from an accelerometer worn on the wrist, and TDS is obtained for a subset of patients who agree to participate at specific investigational centers (n=100) from an accelerometer worn on the ankle. Baseline disease state and demographic information will be obtained at screening.

Another objective for this study is to evaluate the safety of ABS eMDPI use in patients with exacerbation-prone COPD.

The safety endpoints for this study include the following:

- adverse event data
- physical examinations

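### SAP 10.7 states no output for physical examination, a named safety endpoint, and its last sentence files abnormalities already present at screening as adverse events

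*SAP*

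**What the plan says.** SAP 1.1 introduces a two-item list with "The safety endpoints for this study include the following": adverse event data, then physical examinations. Protocol 2.1 has the same list, and Protocol 7 says that "safety will be assessed by qualified study personnel by evaluating reported adverse events and physical examinations".

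Protocol 9.7 plans two outputs that bear on the examination. One is specific: "potentially clinically significant abnormal values (physical examination) based on predefined criteria will be provided as well". The other is general to continuous variables, whose descriptive statistics "will be provided for actual values and changes from baseline to each time point".

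SAP 10.7 gives the timing of the examination (screening, exacerbation visits, final or early termination visit), the body systems covered, and the measurement of weight. It then sets a filing rule: "Any pre-existing abnormality will be reported as a part of medical history and any ongoing abnormality identified at screening and any new findings". The sentence goes on to add clinically significant worsening at a later visit and closes by making all of these, from the ongoing abnormality onward, adverse events. No table, change summary or listing is stated.

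Protocol 7.1.1 takes a different line on findings already there at entry: "Stable chronic conditions (such as arthritis) that are present before study entry and do not worsen during this study will not be considered adverse events". On timing, SAP 10.4 says "Adverse events will be included as treatment emergent based on the date of the baseline", and defines that date as the first dispensing of a device.

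**The concern.** Two faults sit in one short SAP section, and each makes the other worse.

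The first is a missing output. The protocol commits to summarising abnormal examination values and, by its general sentence, weight change. The SAP is the document that programmers follow, and it claims precedence where the two differ. If 10.7 is programmed as it stands, examination results after screening appear in a summary only when an investigator has judged them to be adverse events.

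The second is a defect in that remaining route. Read as written, it admits findings that were present before any study drug was used. In a COPD population with chest signs and comorbidity at entry, such findings are to be expected. Some could then be counted as arising on treatment in a single-arm study that has no control group to expose the error.

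**Working it through.** There is no planned figure to reproduce; the check is a comparison of passages.

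**1. Is there an examination output elsewhere in the SAP?**
- SAP 5.3 summarises weight, height and BMI at baseline only.
- SAP 4.2.2 takes the screening examination and weight as baseline, but no section uses that baseline for a change.
- SAP 5.4 tabulates medical history by system organ class and preferred term, which covers pre-existing findings.
- SAP 10.4 tabulates adverse events, which covers new or worsened findings if they are filed as such.
- SAP 4.6 and 5.1 make general statements about data listings. Neither provides a safety summary.
- Neighbouring safety sections do state an output: deaths (10.5), pregnancy tests (10.6) and concomitant medications (10.8).

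So no section supplies a summary of the examination itself.

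**2. Is the omission recorded?** SAP Section 20 has four entries: the ITT set, the mITT set, the safety set and the predictive models. Physical examination is not among them. The SAP introduction allows a difference to be explained in the SAP or in the clinical study report, so an explanation could still come. None has been given in the plan.

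**3. Which variables are affected?** The predefined criteria mentioned in Protocol 9.7 appear in neither document, so the abnormal-value summary could not be programmed even by going back to the protocol. Weight is the only examination item that is numeric and scheduled after screening (Protocol Table 1 and 7.5). It is also the only repeated numeric clinical safety measure: vital signs are taken at screening and not used for safety (7.6), there is no electrocardiogram (7.7) and no blood is drawn (5.9).

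**4. How much data is this?** From the planning figures, 360 completers each have a final examination, and 91 exacerbations (range 73 to 110) are expected. If each exacerbation leads to one exacerbation visit, post-screening examinations number about 360 + 91 = 451, with a range of 360 + 73 = 433 to 360 + 110 = 470. Early termination visits, at most 400 − 360 = 40, would add to this.

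**5. Where does an abnormality present at screening go?**
- First clause of the SAP 10.7 sentence: if pre-existing, to medical history.
- Second part of the same sentence: if ongoing at screening, to adverse events, together with new and worsened findings.
- Protocol 7.1.1: if stable and present before entry, not an adverse event.

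A stable finding seen at screening meets all three descriptions, so the SAP sentence contradicts both itself and the protocol.

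**6. When would such an entry be treatment emergent?**
- Onset correctly dated before dispensing: not treatment emergent under SAP 10.4.
- Start date missing: treatment emergent under SAP 10.4 and 4.6.
- Start date entered as the screening date, with screening and baseline combined (allowed by Protocol 3.1 and SAP 2.1): the date equals the dispensing date. SAP 10.4 does not say how that day is treated; on the usual on-or-after reading the entry counts, even though the examination may precede the first dose. Protocol 7.1.2 instead starts the treatment-emergent period after the first dose.

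**The case against.** The strongest reply is that little is lost. New or worsened findings filed as adverse events are tabulated overall and by severity and are listed. Pre-existing findings are in the medical history table. Silence in the SAP does not cancel Protocol 9.7, whose commitment arguably still stands. Sites record adverse events under the protocol, not the SAP; nothing in the SAP tells programmers to generate adverse events from examination data; and the filing sentence is probably a drafting slip.

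Most of this is fair and limits the point. A reader might infer that the examination endpoint goes wholly unreported. The documents do not support that, because findings can reach the adverse event and medical history tables. A reader might also infer that long-standing COPD findings will enter the treatment-emergent table in large numbers. That does not follow either: a correctly dated onset keeps them out, and neither document says how many visits are combined or how many patients have abnormalities at screening. Nor does Protocol 9.7 promise a shift table by body system.

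Weight should not be over-read. Protocol 1.2.2 does list it among events judged drug-related in an earlier device study ("including abdominal pain, feeling jittery, irritability, weight increase, tremor, nervousness, coughing, and sneezing"), but with no count and in a mixed asthma and COPD population. Mean change over 12 weeks without a control group would say little about the drug.

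What stands is narrower. A commitment that the SAP neither carries out nor withdraws, with criteria nowhere defined, leaves the programmer without an instruction. A sentence that contradicts the protocol's own definition needs correcting whatever its author intended.

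**Conclusion.** The point holds in limited form. One of the two named safety endpoints has no summary of its own in the SAP. The outputs that Protocol 9.7 promises for it are missing without explanation, and the criteria for one of them are not given. Planning figures suggest about 450 post-screening examinations, assuming one visit per expected exacerbation, whose results would be summarised only through investigator-filed adverse events.

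The filing sentence in SAP 10.7 conflicts with its own first clause and with Protocol 7.1.1. Its effect on the treatment-emergent table depends on someone following it literally and also leaving the start date blank or entering the combined-visit date. The documents give no basis for a count, and the effect may be nil.

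This does not touch the exacerbation analyses. It is a correctable gap in the safety reporting and should be closed before database lock.

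**What to change.** 1. In SAP 10.7, state the Protocol 9.7 output: abnormal examination findings by visit, with the criteria written out, and weight with change from screening at exacerbation visits and visit 5. A shift table by body system is one way to present the findings, but the protocol does not require it. If the summary is being dropped on purpose, record that in Section 20 with the reason.

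2. Reconcile the last sentence of SAP 10.7 with Protocol 7.1.1, so that stable abnormalities present at screening go to medical history and only new or worsened findings count as adverse events.

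The cost is one or two tables from data already collected and one reworded sentence. No visit, assessment or change in patient care is involved.

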10.8. Concomitant Medications or Therapies

Concomitant therapies and medications, including medications that are taken on an as needed basis and occasional therapies, will be monitored during the study. Details of prohibited medications may be found in Section 5.6 of the study protocol. All concomitant medications will be coded using the WHO Drug Dictionary.

The incidence of concomitant therapies and medications will be summarized using descriptive statistics by therapeutic class category and PT term. Patients are counted only once in each therapeutic class, and only once in each PT category. Concomitant therapies and medications for a given patient will include all medications up to the end of the patient's participation in the study (date of completion, withdrawal, lost to follow-up, or death).

A listing of all concomitant therapies and medications by patient and the study day the therapy or medication was started will be provided.

11. TOLERABILITY VARIABLES AND ANALYSIS

Tolerability was not specifically defined for this study.

12. PHARMACOKINETIC ANALYSIS

Not applicable.

13. PHARMACODYNAMIC ANALYSIS

Not applicable.

14. PHARMACOKINETIC/PHARMACODYNAMIC ANALYSIS

Not applicable.

15. BIOMARKER ANALYSIS

Not applicable.

16. IMMUNOGENICITY ANALYSIS

Not applicable.

17. ANCILLARY STUDIES ANALYSIS

Not applicable.

18. PLANNED INTERIM ANALYSIS

Not applicable.

19. STATISTICAL SOFTWARE

All data listings, summaries, and statistical analyses will be generated using SAS® version 9.1.3 or higher.

20. CHANGES TO ANALYSES SPECIFIED IN THE STUDY PROTOCOL

20.1. Intent-To-Treat Analysis Set

Statistical Analysis Plan Section	Protocol Section	Protocol Description	Statistical Analysis Plan Change	Rationale
3.1	9.2.1	The intent-to-treat (ITT) analysis set will include all enrolled patients regardless of whether or not a patient took any IMP. A patient is considered enrolled according to the status reported in the database. This analysis population will be used for summarization of patient disposition.	The intent-to-treat (ITT) analysis set will include all enrolled patients regardless of whether a patient took any investigational medicinal product (IMP). A patient is considered enrolled according to the status reported in the database. This analysis set will be used for endpoint analysis and safety analysis.	Patient disposition will be summarized using all patients entered into the database not just enrolled patients, since all patients are needed to descriptively summarize patients screened, patients screened but not enrolled and reason for non-enrollment. All endpoint and safety analyses will use the ITT analysis set.

20.2. Modified Intent-To-Treat Analysis Set

Statistical Analysis Plan Section	Protocol Section	Protocol Description	Statistical Analysis Plan Change	Rationale
3.2	9.2.2	The modified intent-to-treat (mITT) analysis set is a subset of the ITT analysis set that will include only the patients who used the IMP at any time during the study. This analysis population will be used for endpoint analysis”.	The modified intent-to-treat (mITT) analysis set is a subset of the ITT analysis set that will include patients who used the IMP at any time during the study and patients who did not use the IMP at any time during the study provided these patients complied with study requirements and the ABS eMDPI inhalers were available for data download at the end of the study.	This study is to evaluate the relationship between as-needed usage of ABS eMDPI and CE-COPD/severe CE-COPD. As-needed usage may include no usage if patients' health did not require ABS eMDPI use. Endpoint analyses will be summarized using the ITT analysis set.

